5.3 Managing differences in recruitment rates

Section modified by Amendment 2 (Modification 6).

Overall enrollment will be dependent on availability of Essure.

Recruitment in the Essure arm is planned to continue as long as Essure is available at the study sites and being implanted.

Enrollment in the laparoscopic tubal sterilization arm will be ceased once its enrollment reaches approximately 2:1 ratio laparoscopic tubal sterilization: Essure (anticipated).

5.4 End of study

Section modified by Amendment 2 (Modification 17).

The end of the study as a whole will be reached as soon as the last visit (60-month visit) of the last subject has been reached in all centers.

6. Study population

Section modified by Amendment 2 (Modification 8).

The study population will include subjects of reproductive age, at least 21 years of age, who have not been pregnant within the past 6 weeks.

The Essure study population group will include subjects who chose to undergo hysteroscopic sterilization and who meet the criteria as outlined in the most updated approved Essure IFU.

Subjects seeking laparoscopic tubal sterilization must be considered appropriate surgical candidates by the investigator.

6.1 Inclusion criteria

Section modified by Amendment 2 (Modification 8, Modification 9).

1. Signed and dated informed consent;
2. Subjects who are at least 21 years of age;
3. Subjects of all weights will be included;
4. Subjects who are scheduled to undergo an Essure insert placement procedure for permanent birth control or laparoscopic tubal sterilization. Decision for either treatment based upon clinical practice and physician / patient counseling;

5. For the Essure group only:
 - Subjects selecting hysteroscopic sterilization who are not contraindicated for the Essure procedure according to the most current approved version of the Essure IFU;
 - Subjects must have received the most current approved version of the Patient Information Booklet (PIB) and completed the Essure patient checklist;
 - Subjects selecting Essure who are willing to use alternative contraception for at least 3 months post-Essure placement procedure, until a satisfactory Essure Confirmation Test is documented;
 - Subjects who are believed to have two viable fallopian tubes.
6. For the laparoscopic tubal sterilization group only:
 - Subjects selecting laparoscopic sterilization who are not contraindicated for laparoscopic tubal sterilization according to common clinical practice standard of care;
 - After signed informed consent, subjects must have received the American College of Obstetricians and Gynecologists (ACOG) Patient Information Brochure on Sterilization by Laparoscopy and completed the laparoscopic tubal sterilization patient checklist.
7. Subjects who are willing to accept the risk of pregnancy occurring while relying on the Essure device or laparoscopic tubal sterilization for prevention of pregnancy;
8. Subjects who have the capacity to understand the informed consent, comply with the protocol requirements, and provide reliable feedback during the follow-up period;
9. Subjects who agree to participate in the scheduled study visits;
10. Subjects who are willing to allow data to be shared with the sponsor and with regulatory bodies.

6.2 Exclusion criteria

Section modified by Amendment 1 (Section 16.1) and Amendment 2 (Modification 10, Modification 11).

1. Subjects who are post-menopausal;
2. Subjects suspected of being or who are confirmed to be pregnant;
3. Subjects post-partum or having undergone pregnancy termination ≤ 6 weeks prior to scheduled procedure (Note: subjects may be screened and consented for the study prior to 6 weeks post-partum / post pregnancy termination; however, PRO tools must be administered > 6 weeks post-partum / pregnancy termination and the sterilization procedure must occur > 6 weeks post-partum / pregnancy termination);
4. Subjects uncertain about ending fertility;
5. Subjects with an active upper or lower genital tract infection;
6. Subjects with gynecologic malignancy (suspected or known);

7. Subjects who have had an attempted prior sterilization procedure (either laparoscopic or hysteroscopic);
8. Subjects scheduled to undergo concomitant intrauterine or laparoscopic procedures at the time of insert placement (intrauterine device removal/insertion is not considered a concomitant procedure) or laparoscopic sterilization;
9. Subjects with unexplained vaginal bleeding;
10. Any diseases or conditions that might interfere with the conduct of the study or the interpretation of the results (subjects with pre-existing conditions such as pelvic pain, autoimmune disease, or menorrhagia may be included at the discretion of the principal investigator);
11. Subjects who are direct employees or immediate family members of the Sponsor company or site investigators.

For the Essure group only:

12. Subjects who can have only one insert placed (including contralateral proximal tubal occlusion or suspected unicornuate uterus);
13. Subjects who have a known abnormal uterine cavity that makes visualization of the tubal ostia impossible and / or abnormal tubal anatomy or previous tubal ligation (including failed ligation);
14. Subjects who have had total or partial salpingectomies;
15. Subjects who are currently taking corticosteroids or immunosuppressive therapy;
16. Subjects with a known allergy to all contrast media available for use in HSG.

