- In addition, any subject who experiences an AE of pelvic / lower abdominal pain in this study will be evaluated for possible hypersensitivity / allergic reaction including central laboratory evaluation and case adjudication (see below for further details on hypersensitivity / allergy).

Per the definition by the American College of Obstetricians and Gynecologists, chronic pelvic pain is pain in the pelvic area that lasts for 6 months or longer. In those subjects reporting lower abdominal / pelvic pain at any time during the study, either spontaneously or in response to the regularly scheduled PRO tool and who have been judged to have experienced an AE, it will be determined if duration of the pain meets this definition. The percentage of subjects in each group (laparoscopic and hysteroscopic) who are determined to have new onset or worsening chronic pelvic / lower abdominal pain will be reported. Additional analyses will be carried out looking at total number of pain reports (regardless of chronicity), intensity, and pain interference.

- **Bleeding:** The proportion of subjects reporting AEs of abnormal uterine bleeding (AUB) after insertion of Essure System compared to the proportion of subjects reporting AEs of AUB after laparoscopic tubal sterilization. Total incidence of new onset or worsening abnormal bleeding events will be based on AE reporting. If a potential bleeding AE is reported at a scheduled visit or if the subject spontaneously reports such an event to the site at some other time, the event will be evaluated per standard AE assessment. In the event of a report outside of a scheduled visit or scheduled PRO administration, the Aberdeen Menorrhagia Severity Scale (AMSS) and two intermenstrual bleeding questions will not be re-administered as the recall period for these PRO tools is 3 months and these data are captured during the scheduled PRO tool administration which occurs every 3 months.

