If during the course of a scheduled PRO administration (see [Table 9–2](#) and [Section 9.2.3.1](#)) the subject indicates that she has experienced abnormal bleeding that reaches a preset threshold on the AMSS, even if the subject has not spontaneously reported this event, the investigator will be alerted and instructed to investigate this finding in order to determine whether or not an AE has occurred. Standard criteria for AE assessment (e.g., new or worsening symptom) will be used and all investigators will be trained on standard AE assessment. The threshold for investigation of bleeding as an AE will be a total Aberdeen Scale score of ≥ 40 . Investigation will also be triggered by responses that meet a preset threshold on specified single questions, including those on the two intermenstrual bleeding questions. These are summarized in [Section 9.2.3.1](#). The percentage of subjects in each group (laparoscopic and hysteroscopic) who are determined to have an AE related to AUB will be reported. Not all reports of AUB reported on the PRO will be considered AEs. This is particularly notable in the case of a subject who has pre-existing AUB that continues to be unchanged post-sterilization procedure. Additional analyses will be carried out looking at duration and severity of abnormal bleeding, type of abnormality (e.g., menorrhagia, metrorrhagia), and subject impact based on the PRO tools.

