17.4 Aberdeen Menorrhagia Severity Scale

The following questions ask you about your period during the last three months. Please give a single answer for every question.

1. On average, during the last three months, for how many days did your period last?

- ☐ Less than 3 days
- ☐ Between 3 and 7 days
- ☐ Between 8 and 10 days
- ☐ More than 10 days

2. On average, during the last three months, were your periods regular or irregular?

- ☐ Regular
- ☐ Irregular

3. On average, during the last three months, how many days were there from the first day of a period to the first day of the next period?

- ☐ Less than 21 days
- ☐ Between 21 and 35 days
- ☐ More than 35 days

4. On average, during the last three months, would you describe your periods as?

- ☐ Light
- ☐ Moderate
- ☐ Heavy
- ☐ Very Heavy

5. On average, during the last three months, for how many days of each period was the bleeding heavy?

- ☐ Not heavy
- ☐ Between 1 and 3 days
- ☐ Between 4 and 6 days
- ☐ Between 7 and 10 days
- ☐ More than 10 days

6. On average, during the last three months, have your periods been associated with any pain?

- ☐ No pain at all
- ☐ Slight pain
- ☐ Moderate pain
- ☐ Severe pain
- ☐ Very severe pain

7. On average, during the last three months, have you had any problems with soiling / staining any of the following because of your periods?

- ☐ Soiling / staining of your outerclothes / overgarments
- ☐ Soiling / staining of your bed linen
- ☐ Soiling / staining of your upholstery

8. On average, during the last three months, have your periods prevented you from carrying out your work, housework or other daily activities?

- ☐ No, not at all
- ☐ I could continue to work, but my work suffered
- ☐ Yes, usually with no more than one day with each period
- ☐ Yes, usually more than one day with each period

9. On average, during the last three months, have you been confined to bed with each period?

- ☐ No, not at all
- ☐ Yes, usually for part of one day
- ☐ Yes, usually for the whole of one day
- ☐ Yes, usually for more than one day 0

10. On average, during the last three months, have your leisure activities been affected by your heavy periods? (including sport, hobbies, social life)

- ☐ Not affected by heavy periods
- ☐ Mildly affected by heavy periods
- ☐ Moderately affected by heavy periods
- ☐ Severely affected by heavy periods
- ☐ Heavy periods have prevented any social life at all

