17.5 Intermenstrual questions

Intermenstrual questions

Section modified by Amendment 1 (Section [16.1](#)).

At any time during the last 3 months did you experience any bleeding or spotting in between your periods?	 No  Yes

If yes, how much did it interfere with your normal daily activities?	 Not at all  Mildly  Moderately  Severely

17.6 Short Form – 36

Your Health and Well-Being

This survey asks for your views about your health. This information will help keep track of how you feel and how well you are able to do your usual activities. *Thank you for completing this survey!*

For each of the following questions, please mark an ☒ in the one box that best describes your answer.

1. In general, would you say your health is:

Excellent	Very good	Good	Fair	Poor
				

2. Compared to one year ago, how would you rate your health in general now?

Much better now than one year ago	Somewhat better now than one year ago	About the same as one year ago	Somewhat worse now than one year ago	Much worse now than one year ago
				

3. The following questions are about activities you might do during a typical day. Does your health now limit you in these activities? If so, how much?

	Yes, limited a lot	Yes, limited a little	No, not limited at all
a. Vigorous activities, such as running, lifting heavy objects, participating in strenuous sports	 1	 2	 3
b. Moderate activities, such as moving a table, pushing a vacuum cleaner, bowling, or playing golf.....	 1	 2	 3
c. Lifting or carrying groceries.....	 1	 2	 3
d. Climbing several flights of stairs.....	 1	 2	 3
e. Climbing one flight of stairs.....	 1	 2	 3

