#### **4.6.1 Baseline**

Baseline is generally defined as the last available value at or before the index event.

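### For women 6 to 13 weeks after a delivery or termination, the baseline bleeding questionnaires look back into the pregnancy, yet the SAP accepts them as baseline

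*Protocol*

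**What the plan says.** Criterion 3 in Protocol 6.2 lets women be screened early after a delivery or termination on two conditions: "PRO tools must be administered > 6 weeks post-partum / pregnancy termination" and "the sterilization procedure must occur > 6 weeks post-partum / pregnancy termination". Protocol 9.2.2 places the baseline AMSS and the two intermenstrual questions at the procedure visit.

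Both instruments recall 3 months. The AMSS (Protocol 17.4) opens with "The following questions ask you about your period during the last three months"; the intermenstrual item (Protocol 17.5) asks "At any time during the last 3 months did you experience any bleeding or spotting in between your periods". Protocol 5.2.1 relies on that recall length when it explains why, after an unscheduled bleeding report, the two tools "will not be re-administered as the recall period for these PRO tools is 3 months". SAP 4.6.1 then states: "Baseline is generally defined as the last available value at or before the index event".

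The AUB main endpoint in Protocol 5.2.1 is counted from adverse events judged new or worsening. A total AMSS score of 40 or more, or certain item answers, only prompts the investigator to look. Bleeding reported on the questionnaire is not automatically an event: "This is particularly notable in the case of a subject who has pre-existing AUB that continues to be unchanged post-sterilization procedure".

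**The concern.** The 6-week limit is about half the recall period it is meant to serve. A woman just past it is asked to average her periods over months when she was pregnant or newly post-partum. As printed, the first AMSS question has no answer for having had no period; its lowest option is a period of under 3 days.

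The error could go either way. If her answers reflect absent periods, baseline is too low and the return of ordinary menses can look new. If she scores post-partum bleeding as a long or heavy period, baseline is too high and real worsening can be hidden. AMSS alerts use absolute cut-offs, so an investigator separating new or worse bleeding from unchanged bleeding needs a pre-procedure reference, and the scheduled one is unreliable here. The AUB search list in SAP Table 3 includes absent, delayed and irregular menstruation, terms that are sensitive to how far menses have returned after a pregnancy.

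**Working it through.** The plan states no figure to reproduce, so the check is arithmetic on the recall window.

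**Inputs**
- Earliest baseline: 6 weeks + 1 day (day 43, 6.14 weeks), from Protocol 6.2.
- Recall R: 3 months, from Protocol 5.2.1, 17.4 and 17.5. Taken as 365.25 / 4 / 7 = 13.04 weeks, or about 91 days.
- t: weeks from delivery to baseline.

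**Formulas**
- Weeks of pregnancy in the window: P = max(0, R − t).
- Weeks from the first six post-partum weeks: E = 6 − max(0, t − R), not below 0.
- Later weeks: R − P − E.

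**At the earliest baseline.** In days, 91 − 43 = 48, and 48 / 91 = 53%. In weeks, P = 13.04 − 6.14 = 6.90 (53%), E = 6.00 (46%), and 0.14 weeks (1%) remain.

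| Baseline after delivery | Pregnancy | First 6 post-partum weeks | Later |
|---|---|---|---|
| 6 weeks + 1 day | 53% | 46% | 1% |
| 8 weeks | 39% | 46% | 15% |
| 10 weeks | 23% | 46% | 31% |
| 13 weeks | 0.3% | 46% | 54% |
| 16 weeks | 0% | 23% | 77% |
| 19 weeks | 0% | 0.3% | 99.7% |

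The window is free of pregnancy from R = 13.04 weeks, and of the first six post-partum weeks as well from R + 6 = 19.04 weeks. If 3 months is read as 12 weeks, the first pregnancy share is 5.86 / 12 = 49% and the two limits become 12 and 18 weeks. After a termination, P cannot exceed the length of that pregnancy.

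**Can other baseline items replace the AMSS?**
- The 6-month bleeding items in SAP Table 1 reach into the pregnancy too. With a window of 26.09 weeks, (26.09 − 6.14) / 26.09 = 76% at 6 weeks + 1 day and (26.09 − 13) / 26.09 = 50% at 13 weeks, if the pregnancy was long enough to fill it.
- The Table 1 item on bleeding medication over 2 years reaches further back, but records treatment only.
- The lifetime-history items in Table 1 cover fibroids, adenomyosis and endometriosis, not heavy or abnormal bleeding.
- The screening history of vaginal bleeding and AUB (Protocol 9.2.1) has no stated reference period.

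So relevant history exists, but none of it is scored.

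**Does any analysis isolate these women?** SAP 6.7 has no subgroup by time since birth, and SAP 6.8 varies only the censoring. SAP Table 1 does collect time since last birth or abortion, and SAP 6.6.2 tabulates it in the matched sets.

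**The case against.** A reader might infer that the plan cannot tell whether later bleeding is new or worse in these women. The documents do not support that. The endpoint is an investigator's adverse-event judgement under Protocol 5.2.1 and 9.6.1.1, not an AMSS change score. The investigator can know of the recent birth and has the screening history. Recording ordinary returning menses as an untoward event would take a misjudgement, not just an alert. This stands, and it is why the point concerns the scheduled baseline score and not the endpoint as a whole.

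A reader might also infer that AMSS changes from baseline are corrupted. SAP Table 2 specifies total and item scores and the percentage above 40, and SAP 6.4.6 keeps longitudinal questionnaire data descriptive. Change in AMSS is not a specified output.

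A third inference is that the error differs between arms because time since birth is missing from SAP Table 5. That table lists only likely variables. SAP 6.6.1 considers all baseline variables and adds the rest in a second modelling step, SAP 6.6.2 tabulates Table 1 in the matched sets, and SAP 6.1.1 flags imbalance with p-values. Part of the concern survives: the first-step model is preferred if the extra data contribute little, so balance on time since birth will be visible but is not assured. No arm difference is shown.

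Finally, the study is declared exploratory. That lowers the stakes, but does not make the baseline values interpretable.

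**Conclusion.** The mismatch is real, and the plan has no rule for it. For women who answer from just over 6 weeks to about 13 weeks after a delivery or termination, the recall window contains pregnancy: up to 53% after a delivery, falling to 0% across that range. The baseline is thus mixed to a varying degree, not equally void for all of them. Early post-partum weeks stay in the window until about 19 weeks. The baseline AMSS and intermenstrual answers are not a valid picture of usual bleeding in these women.

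An effect on the AUB endpoint is possible, but its size and direction cannot be computed. The documents give neither the share of women enrolled in this interval nor its split by arm; any share, such as 10% to 30%, would be an assumption. The window figures assume that 3 months is about 91 days and that the pregnancy lasted long enough to fill the part of the window before delivery.

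**What to change.** - **SAP 4.6.1:** use time since last birth or abortion to flag baseline AMSS and intermenstrual values obtained less than 3 months after a delivery or termination as not evaluable. Exclude them from baseline AMSS summaries and from any use in the propensity score. If the score is already built, apply this at the balance reassessments planned in Protocol 10.5.
- **Reporting:** give the number flagged by arm, which supplies the missing share, and point to the balance on time since last birth in the matched set, already tabulated under SAP 6.6.2.
- **SAP 6.8:** add a sensitivity analysis of the AUB endpoint without the flagged women.

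Eligibility and recorded adverse-event judgements stay as they are. An SAP edit cannot revise those judgements, and the documents show no item that records menstrual history specifically before the pregnancy.

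The work is one derived flag from a variable already collected and a few lines of SAP text. The cost is fewer evaluable baseline AMSS values and less precision in the sensitivity analysis. The 3-month cut removes pregnancy from the window but not all early post-partum weeks, which should be stated beside the results.

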6.3 Justification of selection criteria

This is a post-marketing prospective observational cohort study and, therefore, should follow the current standards of care for both hysteroscopic and laparoscopic tubal sterilization procedures in routine practice.

6.4 Withdrawal of subjects from study

6.4.1 Withdrawal

Section modified by Amendment 1 (Section 16.1), Amendment 2 (Modification 12), and Amendment 4 (Modification 3).

Withdrawal criteria

Subjects *must* be withdrawn from the study if any of the following occurs:

- At their own request or at the request of their legally acceptable representative. At any time during the study and without giving reasons, a subject may decline to participate further. The subject will not suffer any disadvantage as a result.

Subjects *may* be withdrawn from the study if the following occurs:

- If, in the investigator's opinion, continuation of the study would be harmful to the subject's well-being.

Depending on the time point of withdrawal, a withdrawn subject is referred to as either “screening failure” or “dropout” as specified below.

Screening failure

A subject who, for any reason (e.g., failure to satisfy the selection criteria), terminates the study before the time point used for the definition of “dropout” (see below) is regarded a “screening failure.”

Re-screening

For subjects considered screening failures, re-screening to enable the subject’s participation at a later time point is allowed once at the discretion of the investigator, provided the subject is eligible at the time of re-screening.

In any case, the investigator has to ensure that the re-screening procedures do not expose the subject to an unjustifiable health risk. Also, for re-screening, the subject will be required to re-sign the ICF, even if it was not changed after the subject’s previous screening. Subjects who re-screen will not be required to repeat screening laboratory assessments if the original screening laboratory assessments were collected within 3 months of the new proposed procedure date.

Dropout

A subject who is eligible for study participation and who has a procedure visit date recorded in the electronic case report form (eCRF) (i.e., the subject shows up for the procedure visit) will be considered to have entered the treatment phase. Any termination after this point for any reason is defined as a “dropout.” Dropouts will not be allowed to re-screen.

Lost to follow-up

A subject will be considered lost to follow-up if she fails to return for 1 scheduled visit and is unable to be contacted by the study site staff.

The following actions must be taken if a subject fails to return to the clinic for a required study visit:

- The site will attempt to contact the subject and reschedule the missed visit and counsel the subject on the importance of maintaining the assigned visit schedule and ascertain if the subject wishes to and / or should continue in the study.
- Before a subject is deemed lost to follow-up, the investigator or designee will make every effort to regain contact with the subject (where possible, 2 telephone calls and, if necessary, a certified letter to the subject’s last known mailing address or local equivalent methods). These contact attempts should be documented in the subject’s medical record or study file.
- Should the subject continue to be unreachable, she will be considered to have withdrawn from the study with a primary reason of lost to follow-up.

- Sites are encouraged to continue attempts to contact lost to follow-up subjects annually to determine whether they wish to resume participation in the study.
- Should the subject return to the site at a later time and wish to continue participation in the study, she will no longer be considered lost to follow-up and should complete the next visit due at that time.

General procedures

In all cases, the reason for withdrawal must be recorded in the case report form (CRF) and in the subject's medical records.

The subject may object to the generation and processing of post-withdrawal data as specified in Section 14.6.

Any subject removed (withdrawn) from the trial will remain under medical supervision until discharge or transfer is medically acceptable.

Details for the premature termination of the study as a whole (or components thereof) are provided in Section 13.

